Subject IDs will be recorded on all pages of case report forms. Protected health information will not be used during data analysis or dissemination. Subjects will only be referred to by their unique Subject IDs.

Data Entry in Database

All subject tracking information will be maintained in a password-protected Excel spreadsheet and REDcap, a HIPAA-compliant (21 CFR Part 11) secure web application on a BSWH computer by trained study staff.

All case report forms and outcomes data will be input into REDcap, a HIPAA-compliant (21 CFR Part 11) secure web application on a BSWH computer by trained study staff.

Data Quality Assurance

Data management functions will occur on a monthly basis and will include data quality checks and verification, as well as internal edit and logic checks (e.g., out of range values, internal inconsistencies). Ten percent of charts will be audited for source document and data entry review. Cross tabulation checks using SAS will also be used. Data will be stored and backed-up periodically on the biostatistician's space on the secure server. Descriptive statistics will be calculated and included into quarterly reports to ensure the quality of data and progress of the study.

Record Retention

All paper source documents will be kept in a double locked storage cabinet in the BSW research office at The Star. All electronic data will be kept on a secure server per federal guidelines. All data will be maintained for two years after study termination per federal guidelines and will be disposed of in accordance to current BSWRI policy.

Management of Subject Safety/ Adverse events

The study staff (PI, Co-Investigators, research coordinators and assistants) will be responsible for collecting and recording all clinical data. As results are collected, all Adverse Events will be identified, graded for severity and assigned causality, reported to the IRB, and compiled for periodic review. After assigning causality, the PI will decide the course of action for the study participant. The PI will evaluate all Adverse Events and determine whether the Adverse Event affects the risk/benefit ratio of the study and whether modifications to the protocol or informed consent form are required. An electronic regulatory binder in REDCap will be used to manage study logs and regulatory documentation. Throughout this process, the PI will inform and collaborate with the research team. The plan to monitor participant data and safety will specifically include the following: (1) [name] will inspect collected data; (2) The IRB offices will be contacted if there is an Adverse Event due to participation; (3) the research protocol will be revised if it is determined that the protocol or intervention presents an unforeseen risk to participants; (4) if an event occurs that requires immediate attention and [name] is unavailable, then members of the research team will follow the emergency procedures put in place by the research team, which may include calling emergency medical services; (5) an invitation to BSW Research Institute Quality Assurance will be delivered to conduct a site visit for internal auditing of procedures and documentation.

Study Withdrawal

Subjects may voluntarily discontinue participation in the study at any time, for any reason.

Protocol Deviations

All protocol deviations will be recorded in the participant's chart and electronic regulatory binder (REDCap) as they occur, and subsequently formally to the IRB at continuing review.

Data Analysis

Participant characteristics will be summarized with means and standard deviations or medians and interquartile ranges for numerical variables, and counts and percentages for categorical variables. The primary outcomes, VO₂ max and test duration, will first be assessed for normality using a Kolmogorov-Smirnov test prior to determining the analysis to be used. If the distribution meets the normality assumption, paired t-tests will be used to determine if there is a difference between participants when wearing and not wearing a face covering. If the distribution does not meet the normality assumption, Wilcoxon signed-rank tests will be used. All secondary outcomes will follow the same analysis plan of assessing the normal distribution assumption to determine the appropriate test for each outcome. Inter-rater reliability analysis will be conducted for the Attitudes for Face Coverings Questionnaire. All analysis will be performed using SAS 9.4 at a 0.05 significance level.

Risks & Benefits

- Physical risks: The potential risks include any and all risks associated with exercise including muscular injury, increased blood pressure and heart rate, and cardiac arrest. Other risks include hypoglycemia post-exercise and lightheadedness or syncope. Although some risks are unavoidable, the careful monitoring of signs and symptoms by the subject and clinical staff will minimize these risks.
- No psychological risks have been identified by participating in this study.
- No social risks have been identified by participating in this study.
- No economic risks have been identified by participating in this study.
- No legal risks have been identified by participating in this study.
- Potential benefits: Participants in this study may experience greater confidence in performing aerobic activities and may gain a better understanding of their personal functional exercise capacity at the time of testing. Participants may also better understand their body's response to exercise with and without a face covering which may impact training and performance in recreational and occupational ventures.

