Therefore, in order to investigate the impact of face coverings on exercise capacity, research will take place in two phases:

Phase I: Participants will be randomized and complete 2 treadmill trials including (1) cardiopulmonary exercise tests (CPET) with face covering, and (2) CPET without face covering.

Phase II: Participants will be randomized and will complete 2 cycle ergometer trials including (1) cardiopulmonary exercise tests (CPET) with face covering, and (2) CPET without face covering. Cognitive testing will occur incrementally as exertion increases.

SPECIFIC AIMS & OUTCOMES

Phase I:

The proposed study consists of 4 specific aims:

Specific Aim 1: Describe the primary and secondary outcomes of athletes during a Cardiopulmonary Exercise Test (CPET) on a treadmill with (arm 1) and without (arm 2) the use of a face covering.

Specific Aim 2: Conduct a randomized crossover trial to determine if there is a significant difference in maximal and submaximal aerobic exercise capacity (VO₂ max; assessed during the CPET) in athletes with (arm 1) and without (arm 2) the use of a face covering.

Specific Aim 3: Describe participants' experiences' while wearing a face covering during exercise.

Specific Aim 4: Determine reliability of the Attitudes Toward Face Coverings Questionnaire

Primary Outcomes:

- VO₂ max during treadmill Cardiopulmonary Exercise Testing (CPET)
- Test duration (time) on a CPET

Secondary Outcomes

- Minute ventilation (VE) at max during CPET

- Subjective dyspnea rating (Borg) at max during CPET
- Subjective exertion rating (Borg) at max during CPET
- O₂ saturation at baseline, each stage, and recovery during CPET
- Blood pressure at baseline, each stage, and recovery during CPET
- Max heart rate during CPET
- Respiratory quotient at max during CPET
- Attitudes Toward Face Coverings Questionnaire
- Scale of Measuring Subjective Perceptions Questionnaire

Phase II:

Specific Aim 1: Describe the primary and secondary outcomes of participants during a Cardiopulmonary Exercise Test (CPET) on a cycle ergometer with (arm 1) and without (arm 2) the use of a face covering.

Specific Aim 2: Conduct a randomized crossover trial to determine if there is a significant differences in cognitive performance outcomes in participants with (arm 1) and without (arm 2) the use of a face covering. Cognitive performance will be measured by simple reaction time and accuracy on the SRT task.

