Specific Aim 3: Describe differences in outcomes between participants with and without previous history of COVID-19 diagnosis

Primary Outcomes:

- VO₂ max during CPET
- Test duration (time) on a CPET
- Reaction time (measured in milliseconds) and percentage accuracy on the SRT task

Secondary Outcomes:

- Minute ventilation (VE) at max during CPET
- Subjective dyspnea rating (Borg) during CPET
- Subjective exertion rating (Borg) during CPET
- O₂ saturation at baseline, each stage, and recovery during CPET
- Blood pressure at baseline, each stage, and recovery during CPET
- Max heart rate during CPET
- Respiratory quotient at max during CPET
- Blood lactate during CPET

[figure not shown]
INVESTIGATIONAL PLAN

Research Design and Methodology

Phase I:

In this prospective, randomized crossover trial of eligible athletes, we will compare VO₂ max during two maximal cardiopulmonary stress exercise tests (CPET), seven to ten days apart. Subjects will be randomized into either the face covering or non-face covering group using a 1:1 randomization scheme, stratified by sex, and will serve as their own control in the subsequent test seven to ten days later (see Figure 1. Randomization diagram, below). A within-subjects analysis will be performed stratified by sex.

[figure not shown]
Figure 1. Phase I Randomization diagram

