**Phase II:**

In this prospective, randomized crossover trial of 50 eligible participants, we will compare two maximal cardiopulmonary stress exercise tests (CPET) on a cycle ergometer, seven to ten days apart, and the impact on cognitive performance. ECG monitoring will take place during exercise testing among individuals with history of COVID-19. Subjects will be randomized into either the face covering or non-face covering group using a 1:1 randomization scheme, stratified by prior COVID-19 diagnosis, and will serve as their own control in the subsequent test (see Figure 2. Randomization diagram, below). A within-subjects analysis will be performed stratified by sex.

Cognitive testing will take place at the end of each stage of the CPET. Cognitive testing using the SACL Cognition application on iPad will include a baseline SRT measurement and additional measurements at the end of each stage of the CPET. The baseline will include a 30s session of SRT for familiarization and then a 30s session will be scored. SRT will then be administered for 30s at the end of each stage of the CPET. The SRT task includes a visual stimulus presented on the touchscreen. Subjects will be instructed to press the stimulus on-screen as quickly as possible. Reaction time and accuracy will be measured on the SRT task. Reaction time is calculated as the average amount of time in seconds between stimulus presentation and user response within a session. Accuracy is calculated as the total number of correct responses to stimuli divided by the total number of stimuli presented during a session (presented as a percentage).

Figure 2. Phase II Randomization diagram

Phase I: Eligibility Criteria

Inclusion Criteria	Rationale
18-29 years of age	Younger and older individuals are excluded to reduce variability of lung volume outcomes. Herdy, A. H. & Uhlendorf, D. (2010) Reference values for cardiopulmonary exercise testing for sedentary and active men and women. Sociedade Brasileira de Cardiologia.

Exclusion Criteria	Rationale
Orthopedic or neurologic, or other limitations	Individuals with limitations that would not allow for exercise testing on a treadmill are excluded.
Previous or current diagnoses for cardiopulmonary conditions	Individuals with conditions for which a healthcare provider has discouraged high-intensity exercise are excluded (e.g., arrhythmia, pacemakers, Wolfe Parkinson White syndrome).

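### The Phase II reaction-time score is not limited to correct responses, so fast wrong touches, if recorded and more frequent in one condition, would bias the masked-unmasked difference

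*Combined protocol and SAP*

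**What the plan says.** The scoring rules are in Research Design and Methodology, Phase II. Participants work on a touchscreen: "Subjects will be instructed to press the stimulus on-screen as quickly as possible". After a scored baseline, "SRT will then be administered for 30s at the end of each stage of the CPET".

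Two adjacent rules define the scores:

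- Reaction time: "Reaction time is calculated as the average amount of time in seconds between stimulus presentation and user response within a session".
- Accuracy: "Accuracy is calculated as the total number of correct responses to stimuli divided by the total number of stimuli presented during a session".

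The Phase II primary outcomes list both measures on one line: "Reaction time (measured in milliseconds) and percentage accuracy on the SRT task". Phase II Specific Aim 2 relies on both: "Cognitive performance will be measured by simple reaction time and accuracy on the SRT task". The Phase II background reads a higher SRT as slower.

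No section gives a minimum or maximum valid time, a rule for early or off-target touches, or a rule for a stimulus with no response. Data Quality Assurance plans general out-of-range checks without limits for SRT. Data Analysis names VO₂ max and test duration as the primary outcomes and does not mention SRT.

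**The concern.** An accuracy score is needed only if some responses are wrong or missing, so the plan itself foresees responses that the reaction-time rule does not deal with. The accuracy rule is restricted to correct responses and the reaction-time rule beside it is not. Taken literally, a premature or misplaced touch that is recorded contributes its time to the mean. If that time is very short, the error lowers the score, and a lower score is read as better.

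Within one condition this is noise. It becomes bias when fast errors are more frequent with the covering than without it, or the reverse. The setting makes such a difference possible: a touchscreen task under instruction to be quick, repeated through a maximal cycle test. The stake is the size, and possibly the sign, of the effect on a primary outcome that serves Aim 2.

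**Working it through.** **The plan's own figure.** There is none to reproduce. The documents give no expected reaction time, SD, target difference or number of stimuli per session for SRT. What follows is sensitivity arithmetic on assumed inputs.

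**Inputs from the documents.** Score = arithmetic mean over responses in a session, with no limit to correct ones; one 30 s session per stage; two conditions compared within person.

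**Inputs assumed.**
- Correct responses without the covering: Normal(300, 40) + Exponential(80) ms, so the mean is 300 + 80 = 380 ms.
- True slowing with the covering: 20 ms, so the mean is 400 ms.
- Wrong touches: uniform on 50-200 ms, mean 125 ms, all recorded as responses.
- Share of wrong touches: 2% without the covering; varied with it.
- No lapses in this part.

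**Formula.** With share *p* wrong, expected score = (1 − *p*) × mean correct time + *p* × 125.

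Without the covering: 0.98 × 380 + 0.02 × 125 = 374.9 ms.

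| Wrong touches with covering | Expected score with covering (ms) | Reported difference (ms) | True difference (ms) |
|---|---|---|---|
| 2% | 0.98 × 400 + 0.02 × 125 = 394.5 | 19.6 | 20 |
| 7% | 0.93 × 400 + 0.07 × 125 = 380.75 | 5.9 | 20 |
| 10% | 0.90 × 400 + 0.10 × 125 = 372.5 | −2.4 | 20 |
| 12% | 0.88 × 400 + 0.12 × 125 = 367.0 | −7.9 | 20 |

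The reported difference crosses zero where 400 − 275*p* = 374.9, that is at *p* = 25.1/275 = 9.1%. Simulated sessions of 12, 20 and 30 stimuli agree with the table. The expected values do not depend on the number of stimuli.

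**Correct responses only.** The mean is 380 ms without and 400 ms with the covering, so the difference is 20 ms in every row. Restricting the mean to correct responses removes the bias; a median is not needed for that.

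**Errors at ordinary latency.** If wrong touches take as long as correct ones in the same condition, the all-response mean stays at 380 and 400 ms and the difference is 20 ms whatever the error rates.

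**Mean or median.** Suppose instead that the covering raises lapses (1-3 s, mean 2000 ms) from 2% to 5% of responses and does nothing else. The mean moves by (0.05 − 0.02) × (2000 − 380) = 48.6 ms. In simulation the session median moves by only about 3 to 4 ms.

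**The case against.** **The bias needs several assumptions together.** The application must record wrong touches as responses, those touches must be fast, and they must be more frequent in one condition. No figure in the documents supports any of these. In a single-stimulus task, a response can reasonably be read as the press on the stimulus itself, in which case off-target touches never enter the mean. This stands, and it is why the finding is conditional. It does not remove the gap, because the text leaves the point to the application.

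**Accuracy already reveals the problem.** It is listed with reaction time, and its denominator is all stimuli presented, so wrong and missed stimuli both lower it. A speed-accuracy trade would therefore be partly visible. That is a real mitigation, but it leaves the reaction-time value unchanged, and the plan gives no rule for reading the two together.

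**Stronger readings that a reader might infer.**
- *Unanswered stimuli are dropped.* The text does not say so. A stimulus without a response has no time to average, but the application could assign a time-out value.
- *One lapse swamps the score.* This depends on the stimulus count and the lapse length, which are not given. With 8-30 responses, typical times of 300-500 ms and lapses of 1-3 s (all assumed), one lapse moves the mean by anything from 3%, (1000 − 500)/30 = 17 ms on 500, to 112%, (3000 − 300)/8 = 338 ms on 300.
- *The median should replace the mean because it gains power.* It does gain power if lapses are stray noise. If lapses are part of the covering's effect, it discards most of that effect, and a slow but correct response leaves accuracy unchanged too. Mean against median is a choice of what to measure, and the documents do not settle it.

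**Conclusion.** The point holds in a limited form. As written, the rule for a Phase II primary outcome does not confine reaction time to correct responses and sets no validity window, although the accuracy rule beside it makes the distinction. Under the assumed inputs, a true slowing of 20 ms would be reported as about 6 ms with 7% fast errors under the covering, and as about −2 ms with 10%. With equal error rates the loss is 0.4 ms; with errors at ordinary latency it is nil.

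These figures illustrate what the rule permits; they do not predict the trial's result. The documents do not support a claim that the score is already biased, that missed stimuli are discarded, or that a median is required. A better definition is available at almost no cost and should be fixed before the data are seen. The seconds in the scoring rule and the milliseconds in the outcome list are only a unit mismatch, to be aligned in the same edit.

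**What to change.** In Research Design and Methodology, Phase II, replace the reaction-time sentence with wording to this effect:

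*Reaction time is the mean time in milliseconds from stimulus presentation to a correct response within each 30 s session. Responses earlier than a pre-set anticipation limit (for example 100 ms) count as incorrect. Incorrect responses and stimuli without a response count against accuracy only and do not enter reaction time.*

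Also:
- State how the application records off-target touches and unanswered stimuli, including any time-out.
- If single responses cannot be exported, use the application's summary for correct responses, if it provides one.
- In that case, do not read a shorter reaction time as better performance when accuracy is lower in the same condition.
- Report the session median of correct responses as a sensitivity analysis. It resists stray long responses but would hide a true increase in lapses, so it should not replace the mean.

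Cost: a few sentences and a response-level export from the iPad application, with no added visits or participants. The score may differ from the application's default output, which the report should say.

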Medical diagnosis of diabetes and/or currently on medications for diabetes (e.g., insulin)	Individuals with a diagnosis of diabetes and/or individuals currently taking medications for diabetes will be excluded, as the results from their VO2max tests would not be comparable to the testing sample.
Uncontrolled asthma	Individuals with conditions for which a healthcare provider has discouraged high-intensity exercise are excluded.
Inmates	Protected population.
Pregnancy	Protected population.
History of previous positive COVID-19 test	Individuals who have previously tested positive for COVID-19 will be excluded from the current study due to possible cardiopulmonary implications.
Presence of beards	Beards interfere with the fit of the Vo2 mask. Therefore, participants with beards will be asked to shave prior to their visit. If they are unwilling to shave, they will not be eligible for the study.
Claustrophobia	Participants who have been diagnosed or treated for claustrophobia will be excluded. Claustrophobia is a contraindication of the CPET test.

Phase II: Eligibility Criteria

Inclusion Criteria	Rationale
18-39 years of age	Younger and older individuals are excluded to reduce variability of lung volume outcomes. Herdy, A. H. & Uhlendorf, D. (2010) Reference values for cardiopulmonary exercise testing for sedentary and active men and women. Sociedade Brasileira de Cardiologia.

Exclusion Criteria	Rationale
Orthopedic or neurologic, or other limitations	Individuals with limitations that would not allow for exercise testing on a treadmill are excluded.
Previous or current diagnoses for cardiopulmonary conditions	Individuals with conditions for which a healthcare provider has discouraged high-intensity exercise are excluded (e.g., arrhythmia, pacemakers, Wolfe Parkinson White syndrome).

Medical diagnosis of diabetes and/or currently on medications for diabetes (e.g., insulin)	Individuals with a diagnosis of diabetes and/or individuals currently taking medications for diabetes will be excluded, as the results from their VO2max tests would not be comparable to the testing sample.
Uncontrolled asthma	Individuals with conditions for which a healthcare provider has discouraged high-intensity exercise are excluded.
Inmates	Protected population.
Pregnancy	Protected population.

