Presence of beards	Beards interfere with the fit of the Vo2 mask. Therefore, participants with beards will be asked to shave prior to their visit. If they are unwilling to shave, they will not be eligible for the study.
Claustrophobia	Participants who have been diagnosed or treated for claustrophobia will be excluded. Claustrophobia is a contraindication of the CPET test.
Currently experiencing symptoms of COVID-19 or < 7 days since last symptoms	Participants will be screened for COVID-19 symptoms using the BSW COVID-19 screener; if participants have past history of COVID-19 based on laboratory testing, participants will be ineligible if <7 number of days since last symptoms

Study Procedures

Phase I & II Subject Recruitment

Up to 100 participants (50 for each phase) will be recruited from Baylor Scott & White Sports Therapy and Research at The Star in Frisco, Texas through approved fliers, calls, emails, and social media, as well as through local community organizations, healthcare clinics, and collaborating centers and organizations, including but not limited to the Sports Academy and the University of North Texas. IRB-approved fliers will be posted at BSW The Star and at affiliated organizations and collaborators in the DFW Metroplex and surrounding areas. In addition, members of the study team will attend meetings with local clinicians and community partners to inform them of the purpose of the study. The study flier will contain information on the study and methods to contact the study team including (1) a QR code linked to the eligibility screener which will be stored in a REDcap, a HIPAA-compliant (21 CFR Part 11) secure web application, (2) a phone number, and (3) an email address of the study coordinator. Interested individuals may contact the study team by phone or email to learn more about the study and undergo a telephone screener or follow the QR code to complete the eligibility screener electronically. A snowball sampling technique will be used for further recruitment whereby interested participants will be invited to ask other athletes they know to contact the study team about participation. Eligible individuals will be contacted by a member of the study team to schedule their first study visit. It is anticipated that recruitment will take 2-4 weeks during each phase to achieve our desired sample size.

Subject Information and Screening

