Eligible individuals will be screened by trained study coordinators via telephone using the Eligibility Script. If a participant is ineligible based on the screening tool, they will be thanked for their time and informed that they are not able to participate further. If a participant is eligible based on the screening tool, they will be asked to schedule a baseline assessment appointment where informed consent will be obtained. All individuals will be given a screening ID number and all screening information will be input into a password-protected subject tracking database.

COVID-19 Screening

Participants will be instructed to wear face coverings from the parking lot and inside the building. Prior to participation in the CPET, subjects will complete the BSWH COVID-19 screening (procedure outlined in supplementary materials) and a temperature check with a TIR-1 thermometer (procedure outlined in supplementary materials) outside of testing environment. If the subject screens positive or has a temperature of over 100 degrees, subject will not be able to participate in the study and instructed to leave the facility and

comply with current state and local recommendations. If the subject screens negative on both assessments, subject will be taken into testing area for CPET testing.

Informed Consent

Informed consent will be obtained by study staff in person at the beginning of their study visit and prior to any study related procedures taking place. Informed consent will be conducted in a private location using similar procedures as described above by trained study staff to minimize coercion. Participants will be informed about the study, have sufficient time to review the consent form, and all study questions will be answered prior to signature. Participants will be given sufficient opportunity to decide whether or not they want to participate. If the participant elects to enroll in the study, they will be instructed on how to sign the consent form and a copy will be given to them prior to the initiation of any study procedures.

Randomization

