A standard cycle ergometry ramp protocol⁷ will be designed for each participant as used in previous masking study.⁸ The initial workloads and incremental increases will be determined based on the subject's age and weight. The protocol consists of 1 minute of unloaded cycling, followed by a 2-minute warmup at 25 W. The exercise phase consists of continuous progressive increases in power output (25 W · min⁻¹) every three minutes until the subject is unable to maintain 50 rpm. This is followed by 4 min of active recovery at 20 W.

- The Borg Rating of Perceived Exertion (6-20) scale will be used during the test to assess subjective exertion
- The Modified Borg Dyspnea Scale (0-10) will be used to assess subjective shortness of breath.
- Intermittent blood pressure measurements and pulse oximeter measurements will be taken by an exercise physiologist and heart rate will be monitored constantly.
- Blood lactate will be measured pre and post-CPET using a Nova Medical Lactate Plus: Blood Lactate Measuring Meter-Version 2 device.

Testing will be terminated if any of the following occurs: (a) subject becomes symptomatic; (b) pain is reported; (c) subject wishes to terminate test; (d) unsafe drop in blood pressure or hypertension over 250/120 mmHg reported; or (e) subject reports a “20” on Borg RPE scale or “10” on Dyspnea scale. Other termination of the test is reserved for the clinical judgment of research staff to ensure safety of the subject. After termination of the test, subject will be instructed to perform a cycling cool-down of 3 to 5 minutes. After subject has completed cool-down, recovery blood pressure, heart rate and pulse oxygenation will be measured and recorded. After completion of the first test, subject will be scheduled for second CPET 7-10 days later to allow for adequate recovery. When data collection is complete, CPET data will be gathered from metabolic cart and matched with subject testing materials.

Disinfection Procedures

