Visit 2	
 COVID-19 screening and temperature check is performed Attitudes Towards Face Coverings Questionnaire ECG among individuals with history of COVID-19 Cardiopulmonary exercise testing (CPET) 
 Heart rate Dyspnea scores Exertion scores Pulse oximetry measurements Blood pressure measurements Lactate measurements (pre and post-CPET) When subject is randomized to face covering: Qualitative question describing experience Quantitative and qualitative questions about difficulty of wearing face coverings during CPET and differences completing the CPET with and without a face covering. Scale of Measuring Subjective Perceptions

Compensation and Costs

While we will not pay participants for taking part, participants will be reimbursed a \$50 Visa gift card for their time/effort to attend each of the assessments (two) which are required for research for a total of \$100. Participants will be given the option to keep their face covering that was given to them during CPET testing. Participants will not incur any additional research-related costs due to study participation.

Data Protection & Confidentiality

In order to assure participant confidentiality, all participants will be assigned a unique study identification number. Only one master list will be maintained by the PI and the study coordinator on a secure network drive in a password protected file. All case report forms and databases will use the subject ID number rather than names or other private health information and entered into REDCap. All paper documentation, including

signed paper consent forms and case report forms will be maintained by the PI behind a locked door in a locked file cabinet.

All participants that are screened will be given a screening identification number. Screening reports will not use private health information and will only refer to patients using the screening identification number. After consent, participants will be given a unique subject ID. All documents thereafter will refer to the participant by subject ID. All screening and enrollment data will be tracked on a password protected enrollment tracking spreadsheet which will also contain the link to identifiers. Only authorized study personnel will have access to this database. All data will be shared on the secured Baylor Network Onedrive server.

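### The Phase II COVID-19 exclusion counts its 7 days only from last symptoms, so a recent positive test in someone who never had symptoms does not exclude

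*Combined protocol and SAP*

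**What the plan says.** The exclusion table under Phase II: Eligibility Criteria has one row on COVID-19. The criterion is "Currently experiencing symptoms of COVID-19 or < 7 days since last symptoms". The rationale refers to the health system's screener for symptoms and continues: "if participants have past history of COVID-19 based on laboratory testing, participants will be ineligible if <7 number of days since last symptoms".

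The corresponding Phase I row works differently. It excludes on the test result, however old and whether or not there were symptoms: "Individuals who have previously tested positive for COVID-19 will be excluded from the current study due to possible cardiopulmonary implications". Phase II cannot keep that rule, because its Specific Aim 3 compares people with and without a previous diagnosis, and its design section stratifies on that history.

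Other checks come before the exercise test:

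- Under Subject Information and Screening, "Eligible individuals will be screened by trained study coordinators via telephone using the Eligibility Script". The recruitment section also describes an electronic eligibility screener.
- Under COVID-19 Screening, a screening questionnaire and a temperature check come before each test, with this consequence: "If the subject screens positive or has a temperature of over 100 degrees, subject will not be able to participate in the study". The procedure is in supplementary materials that are not part of the documents.
- The Phase II Schedule of Assessments lists this at both visits: "COVID-19 screening and temperature check is performed".

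**The concern.** A waiting period after infection needs a starting date for every kind of case it is meant to cover. The row supplies one for people who had symptoms and none for people who did not. The rationale shows that laboratory-confirmed cases were in mind, yet it still counts from symptoms alone.

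Participant and staff safety are at stake, along with a rule that coordinators can apply consistently. If the unseen screeners do not ask about a recent positive test, a person in the first days after one could go on to a maximal exercise test with no wait, close to the staff who fit the mask and take the measurements. Two coordinators reading the printed row could also decide the same case differently.

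**Working it through.** The protocol gives no figure to reproduce. The check applies the row to cases, looks for another row that covers the gap, and then counts the cost of closing it.

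**Step 1: apply the row.** It has two triggers: symptoms now, or fewer than 7 days since last symptoms.

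| Case | Symptoms now? | Under 7 days since last symptoms? | Excluded? |
|---|---|---|---|
| Symptomatic today | yes | not needed | yes |
| Symptoms ended 3 days ago | no | yes | yes |
| Symptoms ended 7 or more days ago | no | no | no |
| Positive test 3 days ago, never symptomatic | no | no date to count from | **no** |

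The last line is the gap. The rationale does not close it, because its laboratory-history clause uses the same starting date.

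**Step 2: look for another row.** Phase I prints 9 exclusion rows: physical limitations, cardiopulmonary diagnoses, diabetes, uncontrolled asthma, inmates, pregnancy, previous positive COVID-19 test, beards and claustrophobia. Phase II also prints 9. Eight are shared, and the positive-test row is replaced by the symptom row. The number of Phase II rows that state an interval from a positive test is 0 of 9. The cardiopulmonary row cannot be stretched to cover it: Phase I has the same row and still needed a separate one for COVID-19.

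**Step 3: effect of a test-date clock at entry.** With a 7-day rule, a volunteer waits at most 7 days from the test. The recruitment section plans 2-4 weeks of recruitment per phase, so the wait fits inside it.

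**Step 4: effect between visits.** Phase II CPET Procedures say: "After completion of the first test, subject will be scheduled for second CPET 7-10 days later to allow for adequate recovery". Let *d* be the day of a symptom-free positive test, counted from Visit 1 and falling before Visit 2, and let *L* be the required interval. Then

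earliest Visit 2 = max(7, *d* + *L*).

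| *L* | *d* | Earliest Visit 2 | Within days 7-10? |
|---|---|---|---|
| 7 | 0 | max(7, 7) = 7 | yes |
| 7 | 3 | max(7, 10) = 10 | yes |
| 7 | 4 | max(7, 11) = 11 | no |
| 10 | 0 | max(7, 10) = 10 | yes |
| 10 | 1 | max(7, 11) = 11 | no |

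Under a 7-day rule, a positive test on days 0-3 leaves the window usable and one on day 4 or later does not. Under a 10-day rule only day 0 does. The existing last-symptoms clock has the same effect if it is rechecked at Visit 2.

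**The case against.** The strongest reply is that the row is one check among several. The visit-day screening turns away anyone who screens positive, and the telephone script and electronic screener come earlier. Any of them may ask about recent tests, and none can be read here. That stands, and it is why the point is confined to the row's wording. It does not settle the matter the other way, because the row itself describes the screener as one for symptoms, and a temperature check need not detect someone without any.

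Staff would also usually learn of a disclosed diagnosis. It is a stratification factor in the design section, it triggers an ECG, and the Visit 1 schedule lists COVID-19 history-taking ahead of the exercise test. This lessens the concern, but the listed items do not include a test date, and the history is not made an eligibility rule.

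The Phase I row is limited support. Its stated reason is a history of infection, with no reference to how recent it was, and a 7-day wait would not answer that reason. The case for a test-based clock rests instead on the Phase II row, which already accepts that a wait is needed and leaves it undefined for one kind of case.

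Finally, the documents do not fix the right interval from a test. That is a clinical choice.

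**Conclusion.** The concern holds as a minor point about one eligibility row. As printed, the row does not exclude a never-symptomatic person with a recent positive test, and no other Phase II row does.

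The number affected cannot be estimated. The documents do not say how many Phase II volunteers will have a history, when they tested, or how many had no symptoms. It is likely to be small.

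Confidence is high about the wording. Whether such a person would actually reach the exercise test depends on screening content that is not shown. If that content already covers recent positive tests, only the wording needs attention.

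Harm is limited by face coverings indoors, the ECG for people with a history, a defibrillator at hand, the stopping rules and the disinfection procedure, but none of these sets a waiting time. The mask versus no-mask comparison under Data Analysis is paired within person and is not biased by this gap.

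**What to change.** Reword the row to exclude anyone with current symptoms, or with less than 7 days since the later of last symptoms or most recent positive COVID-19 test. The sponsor's clinicians may set a longer interval.

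Apply the same check within the COVID-19 screening already scheduled at both visits. If that screening already asks about recent positive tests, it is enough to say so in the row.

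State that Visit 2 may fall after day 10 for this reason, and record when it does.

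The cost is one reworded row and at most one added screening question. A few volunteers would be delayed briefly, and Visit 2 would occasionally fall outside its window, as counted above.
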